4.5.1. Discontinuation of Study Treatment

If premature discontinuation of study treatment occurs for any reason, the patient should continue attending remaining study visits while off study treatment. The patient will continue to receive study provided OCS (prednisone) treatment for the remainder of their participation in the study. The patient should not be considered withdrawn from the study due to interruption or discontinuation of study treatment. For this study, it is very important to continue collecting data from all patients whether or not they complete treatment.

If premature discontinuation of study treatment occurs, the patient should return to the clinic as soon as possible for a study treatment discontinuation visit. All evaluations should be performed as specified in the protocol for the early withdrawal visit (see Table 5). The investigator must determine the reason for and the date of discontinuation of study treatment and record this information in both the source documentation and the Study Drug Treatment Completion CRF. The patient's continued participation in the study must be discussed by the investigator and site staff with the patient; the investigator and site staff must also request the patient to continue attending study visits according to the study visit schedule with all assessments completed up to week 24 (visit 19). The OCS dose and safety assessments at week 24 (visit 19) are the priority assessments for patients that prematurely discontinue study treatment. At a minimum, the investigator should make every effort to obtain information regarding serious adverse events, OCS dose, and survival status at week 24. A safety follow-up visit (visit 20) should be conducted 8 weeks after visit 19.

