7.1.8. Withdrawal Due to an Adverse Event

Any patient who experiences an adverse event may be withdrawn from the study or from study treatment at any time at the discretion of the investigator. If a patient is withdrawn wholly or in part because of an adverse event, both the adverse events page and termination page of the CRF will be completed at that time.

The patient will be monitored at the discretion of the investigator (eg, until the event has resolved or stabilized, until the patient is referred to the care of a health care professional, or until a determination of a cause unrelated to the study drug or study procedure is made). The investigator must inform the clinical project physician (CPP)/clinical leader as soon as possible of all patients who are being considered for withdrawal due to adverse events. Additional reports must be provided when requested.

If a patient is withdrawn from the study or study drug for multiple reasons that include adverse events, the termination page of the CRF should indicate that the withdrawal was related to an adverse event. An exception to this requirement will be the occurrence of an adverse event that, in the opinion of the investigator, is not severe enough to warrant discontinuation but requires the use of a prohibited medication, thereby requiring discontinuation of the patient. In such a case, the reason for discontinuation would be need to take a prohibited medication, not the adverse event.

If possible, a blood sample for measurement of serum reslizumab concentrations will be obtained from patients experiencing an adverse event leading to withdrawal, a serious adverse event, an

observation of any severe hypersensitivity reaction (eg, anaphylaxis), or an exacerbation of asthma symptoms.

Withdrawal from the study due to worsening of asthma or a CAE will be considered a withdrawal due to lack of effect, not a withdrawal due to an adverse event.

A patient should only be designated as lost to follow-up if the site is unable to establish contact with the subject after 3 documented attempts via 2 different methods (phone, text, e-mail, certified letter, etc).

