6.2. Primary Efficacy Variable(s) and Analysis

6.2.1. Variable Definition

The primary efficacy variable for this study is the categorized percent reduction in the daily OCS dose during weeks 20 to 24 as compared with the OCS dose at the end of the optimization phase.

The week 20 to 24 maintenance dose and corresponding values for absolute and percent change (reduction) from baseline will be calculated as follows:

- **Baseline dose** = the prescribed optimized OCS dose following the OCS optimization period ([Table 8](#))
- **Maintenance dose** = mean of all daily OCS doses during the maintenance period extending from Week 20 to Week 24 ([Table 8](#))
- **Absolute reduction** = maintenance dose – baseline dose
- **Percent reduction** = $100 \times (\text{absolute reduction} / \text{baseline dose})$

For both the primary and secondary efficacy analyses, OCS dose will refer to the total daily dose of oral prednisone prescribed for asthma (as per CRF), unless otherwise noted.

The 5 categories for the primary analysis of percent reduction during weeks 20 to 24 are:

- 90% to 100% reduction
- 75% to <90% reduction
- 50% to <75% reduction
- >0% to <50% reduction
- No decrease in OCS, or loss of baseline asthma control during weeks 20 through 24, or discontinuation from study drug

Loss of baseline asthma control will be defined as FEV₁ value of <80% of baseline at the week 24 visit, or clinically significant worsening in ACQ-6 score (increase ≥ 0.5) at the week 24 visit compared with baseline, and/or clinical asthma exacerbation during weeks 20 through 24 (CAE defined in [Section 6.3.3.1](#)).

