APPENDIX A. IMPUTATION AND ANALYSIS STEPS FOR SENSITIVITY ANALYSIS OF THE PRIMARY VARIABLE

The following represents an outline of the planned methodology for the multiple imputation procedure for the sensitivity analysis of the primary OCS response variable. Minor deviations from this outline can be addressed in the discussion of the results in the CSR. In the situation that more significant updates are warranted, changes will be addressed in a SAP amendment to be finalized prior to database lock.

Step 1: Seed generation.

The seed generation utilized the code below, resulting in a seed (49476) that will be used in the analysis after unblinding.

```
data seed;
  seed = int(time());
  put seed=;
  call symput('seed', left(seed));
run;
```

Step 2: Classify patients with missing data.

Patients in this study will be partitioned into the following 3 categories:

1. ET0; patients who completed all 24 weeks of treatment
2. ET1; patients who withdrew early from treatment but remained in the study contributing post-treatment follow-up data through week 24
3. ET2; patients who withdrew early from treatment but elected not to remain in the study through week 24

Step 3: Imputation of missing data.

Missing values for OCS dose (continuous) at week 24 and at visits in which earlier OCS doses were missing will be imputed. The missing OCS dose will be imputed based on measurements observed at previous visits and treatment group, assuming data are missing at random (MAR). The resulting observations at week 24 will be categorized as per the primary endpoint.

If the pattern of missing data is monotonic, the MONOTONE method in PROC MI will be used for imputation with a linear regression technique.

```
proc mi data=&indata out=&outdata nimpute=10 seed=&seed;
  class treatment;
  monotone regression (week4=treatment base /details);
  monotone regression (week8=treatment base week4 /details);
  monotone regression (week12=treatment base week4 week8 /details);
  monotone regression (week16=treatment base week4 week8 week12 /details);
  monotone regression (week20=treatment base week4 week8 week12 week16 /details);
  monotone regression (week24=treatment base week4 week8 week12 week16 week20 /details);
  var treatment base week4 week8 week12 week16 week20 week24;
run;
```

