If the pattern of missing data is not monotonic, the MCMC MONOTONE method can be selected to transform the missing data pattern to a monotonic missing data structure by filling in missing values for earlier visits that have lower rates of missing data (ie, MCMC MONOTONE as a preliminary step, to be followed by application of the MONOTONE method in PROC MI).

```
proc mi data=&indata out=&outdata nimpute=10 seed=&seed;
  mcmc impute=monotone NBIter=2000 NIter=10000;
  var base week4 week8 week12 week16 week20 week24;
  by treatment;
run;

proc mi data=&outdata out=&outdata2 nimpute=1 seed=&seed;
  class treatment;
  monotone regression (week4=treatment base /details);
  monotone regression (week8=treatment base week4 /details);
  monotone regression (week12=treatment base week4 week8 /details);
  monotone regression (week16=treatment base week4 week8 week12 /details);
  monotone regression (week20=treatment base week4 week8 week12 week16/details);
  monotone regression (week24=treatment base week4 week8 week12 week16 week20/details);
  var treatment base week4 week8 week12 week16 week20 week24;
  by _imputation_;
run;
```

After this step, 10 datasets with complete data have been created.

Step 4: Re-run the primary analysis model.

Percent change from baseline and the corresponding 5-level response variable will be computed based on the imputed dose values at week 24. The proportional odds model will be fitted to the complete set of data for each of the 10 imputed datasets using the same covariates that were used for the primary analysis.

Step 5: Multiple imputation and associated combining rules applied to propagate imputation uncertainty (Little and Rubin 2002).

The output datasets from Step 4 will contain inferential statistics for each imputation iteration. The SAS[®] procedure PROC MIANALYZE will be used to generate an overall p-value and 95% CI for the odds ratio.

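### The Appendix A and B imputation analyses score patients who left the study on OCS dose alone, so loss of asthma control cannot count against them; for stoppers who stayed in the study the scoring rule is contradictory

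*SAP*

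**What the plan says.** SAP 6.2.1 defines the lowest of the five levels as "No decrease in OCS, or loss of baseline asthma control during weeks 20 through 24, or discontinuation from study drug". Loss of control means a low FEV1 or a worsened ACQ-6 at week 24, or a CAE in weeks 20 to 24. The primary analysis (SAP 6.2.2) places every early stopper in this level.

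Appendix A is the check that uses data after drug discontinuation. Step 2 separates completers (ET0), stoppers followed to week 24 (ET1) and stoppers who left the study (ET2). Step 3 says "Missing values for OCS dose (continuous) at week 24 and at visits in which earlier OCS doses were missing will be imputed". The monotone-regression code lists only "var treatment base week4 week8 week12 week16 week20 week24", so FEV1, ACQ-6, CAE status and reason for withdrawal play no part.

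The scoring rule appears in three places:

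- Step 3: "The resulting observations at week 24 will be categorized as per the primary endpoint".
- Step 4: "Percent change from baseline and the corresponding 5-level response variable will be computed based on the imputed dose values at week 24".
- SAP 6.2.3 (and Protocol 9.5.6.2): patients are classified by percent dose reduction at 24 weeks, whether or not they stopped early. Asthma control is not mentioned.

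Protocol 4.5.1 asks stoppers to complete all assessments to week 24, but the fallback is to "obtain information regarding serious adverse events, OCS dose, and survival status at week 24". Appendix B reuses the Appendix A imputations and adds a positive shift to the imputed dose in the reslizumab arm only.

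**The concern.** In this trial a low dose at withdrawal is not evidence of benefit by itself. The protocol tapers the dose, and loss of control may be the reason the patient leaves; Protocol 7.1.8 foresees this: "Withdrawal from the study due to worsening of asthma or a CAE will be considered a withdrawal due to lack of effect". FEV1 and ACQ-6 are measured and CAEs assessed at every treatment visit (Protocol Table 5), yet the imputation model ignores them. A patient whose last doses were low is likely to receive a low imputed dose and to be classed by that dose alone.

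Appendix A is the main check on the rule that every stopper is a nonresponder. If it cannot register loss of control in the patients it imputes, it answers a different question from the primary objective, which is dose reduction without loss of asthma control. In Appendix B the shift is in milligrams of dose, so a large tipping point could be read as robustness although loss of control would give the same category with no shift.

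**Working it through.** **1. The plan's own figure.** Inputs from SAP 2.3: placebo shares 10.9, 7.9, 14.8, 10.8 and 55.6%, common odds ratio 2.63, 76 per group, 90% power; two-sided 0.05 from SAP 4.3. At the lowest cut the placebo odds of a better category are 0.444/0.556 = 0.799. Multiplied by 2.63 this is 2.100, so the reslizumab lowest category is 1/(1 + 2.100) = 32.3%. The full reslizumab distribution is 24.3, 13.5, 19.3, 10.7 and 32.3%. Whitehead's formula gives

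N = 12(1.960 + 1.282)² / [(ln 2.63)² × (1 − Σp̄³)] = 126.1 / (0.935 × 0.902) = 149.4,

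or 75 per arm against the stated 76. The figure reproduces and is not affected by this point. These distributions are the base for step 4.

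**2. One patient.** Take an optimized dose of 20 mg, tapered to 5 mg at the third step of Protocol Table 3, followed by loss of control and complete withdrawal.

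| Week-24 value | Reduction | Category by dose alone |
|---|---|---|
| 5 mg | 15/20 = 75% | second best |
| 7.5 mg (2.5 mg above pre-burst, Protocol 3.1.4.1) | 12.5/20 = 62.5% | third |
| Primary analysis rule | not used | lowest |

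In Appendix B an imputed 5 mg reaches the lowest category only at a shift of 20 − 5 = 15 mg.

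**3. How often the imputation does this.** The documents give no dropout rate and no dose paths, so this is illustration only. Assumptions: Table 3 tapers with a 40 to 70% chance of a successful step at each visit, 10 to 20% of patients in ET2 with doses missing from week 16 or week 20, and the Appendix A sequential regressions. Among simulated ET2 patients already at a reduction of 50% or more, 57 to 86% were imputed into a category of at least 50% reduction and 2 to 10% into the lowest. Among all ET2 patients, 4 to 18% fell in the lowest category, against 100% under the primary rule.

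**4. Effect on the odds ratio.** Assume a share f of the lowest category is loss of control on a reduced dose. For patients scored on dose alone, move f of the lowest category to the other four levels in proportion. Their lowest-category share becomes 55.6(1 − f)% on placebo and 32.3(1 − f)% on reslizumab: 44.5 and 25.8% at f = 0.2; 27.8 and 16.1% at f = 0.5. Mix these patients into each arm at rate d, so the arm's lowest share is multiplied by (1 − d·f), and refit the proportional odds model to the expected proportions.

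| d placebo / d reslizumab | f = 0.2, true 2.63 | f = 0.5, true 2.63 | f = 0.2, true 1 | f = 0.5, true 1 |
|---|---|---|---|---|
| 5% / 15% | 2.67 | 2.73 | 1.04 | 1.10 |
| 15% / 5% | 2.51 | 2.35 | 0.96 | 0.91 |
| 5% / 5% | 2.61 | 2.58 | 1.00 | 1.00 |
| 15% / 15% | 2.57 | 2.49 | 1.00 | 1.00 |

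The estimate rises when reslizumab has more such patients and falls when placebo has more. With equal rates a null effect stays null and a true effect shrinks slightly.

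**The case against.** The strongest reply has four parts.

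First, a reader might infer that no early stopper can ever fail for loss of control. The documents do not support that. ET1 patients are asked for all assessments to week 24, and Step 3 points to the primary endpoint, whose lowest level includes loss of control. For ET1 the defect is a conflict of wording. It becomes a gap only where no more than the Protocol 4.5.1 minimum is retrieved. This part of the reply stands.

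Second, SAP 6.2.3 can be read as dose-only scoring for everyone, completers included: a different but symmetric question. That is possible, so it should not be said that the plan deliberately sets a composite in completers against dose alone in stoppers. But it contradicts Step 3. Step 3 cannot be taken literally either, because the primary endpoint's lowest level also includes discontinuation, which would send every stopper there and leave nothing to impute for.

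Third, a reader might infer that the patient in the example is always scored as a good responder. The imputed value is a random draw and may reach baseline, earlier doses may already have been raised, and 5 mg of 20 mg lies exactly on a category boundary. The outcome is possible, and often likely, but not automatic.

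Fourth, Appendix B leaves placebo at MAR and penalizes only reslizumab, so favourable dose-only scoring of placebo stoppers makes that test harder for reslizumab. This limits the harm, but the shift still cannot represent loss of control on a low dose.

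**Conclusion.** The point holds for ET2 patients: Appendix A gives them no asthma-control status, so they cannot enter the lowest category for that reason, and one who tapered, lost control and withdrew can be scored as a responder. For ET1 patients the SAP does not say whether observed loss of control overrides the dose category. Appendix B inherits both problems.

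The reach is limited. A reader might infer that the primary result is in doubt; it is not, because SAP 6.2.2 puts all stoppers in the lowest category, and the Wilcoxon analysis in SAP 6.3.2.2.3 ranks withdrawals and loss of control below every observed reduction. The effect on the sensitivity odds ratio is modest and has no fixed direction: 2.51 to 2.67 around 2.63 at a 20% control-failure share with three-fold unequal dropout, and 2.35 to 2.73 at a 50% share. These ranges rest on assumed dropout rates and on an assumed split of the 55.6%, which itself already includes discontinuation. They show scale and are not forecasts. The change is worth making because the stated rule can give a category that contradicts the endpoint, and correcting it is cheap.

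**What to change.** 1. In Appendix A, state that observed loss of control (FEV1, ACQ-6 or CAE) puts any patient, ET0 or ET1, in the lowest category whatever the dose, and that discontinuation alone does not do so in this analysis.
2. Where week-24 control status is missing, impute a loss-of-control indicator together with dose in Step 3. Use a small set of predictors already collected, for example last FEV1 as a percentage of baseline, last ACQ-6 change and any on-study CAE. In Step 4, place patients with imputed loss of control in the lowest category.
3. Use the same datasets in Appendix B.
4. Align Step 4 and SAP 6.2.3 with Step 3, so that one scoring rule remains.

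Cost: SAP wording and some programming; Appendix A already allows an SAP amendment before database lock. No new data item is needed, since Protocol 4.5.1 already asks attending stoppers for all assessments. The model must stay simple because few patients are likely to be imputed, and it still relies on MAR. Responder shares among imputed patients will be slightly less favourable.

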APPENDIX B. TIPPING POINT ANALYSIS

The tipping point analysis evaluates several combinations of imputed missing data values until the analysis reaches a “tipping point” or point at which a particular combination of imputed missing data changes the study conclusions, as summarized by its p-value. This is a sensitivity analysis utilizing multiple imputations under the missing not at random (MNAR) assumption, and will only be conducted if a significant result ($p \leq 0.05$) is observed as part of the primary analysis. If the sensitivity analysis reveals that the tipping point consists of unreasonable values, then the robustness of the study results is supported. This is in accordance with the recommendation discussed in the "Prevention and Treatment of Missing Data in Clinical Trials Report" ([National Research Council 2010](#)).

The following represents an outline of the planned methodology for the “tipping point” multiple imputation sensitivity analysis of the primary response variable (OCS dose). Minor deviations from this outline can be addressed in the discussion of the results in the CSR. In the situation that more significant updates are warranted, changes will be addressed in a SAP amendment to be finalized prior to database lock.

Imputations will be performed for the missing OCS dose at week 24 and the resulting observations will be categorized as per the primary endpoint. OCS dose will be imputed for patients who discontinued treatment prior to the endpoint of the study. Multiple imputation and associated combining rules will be applied to propagate imputation uncertainty (see [Appendix A](#) for additional details). In the following analysis, the OCS dose in the control group will be imputed assuming that missing data are MAR. For the treatment group, the OCS dose will be imputed in the same manner, but then a constant shift (>0) will be added to the imputed values to allow for MNAR. In the treatment group, this shift will be progressively increased and the process repeated until the treatment effect is no longer significant at the 5% level. The value of the shift parameter at which the treatment effect is no longer significant is called the “tipping point”.

The tipping point analysis will be performed according to the following steps.

1. Missing values will be imputed assuming MAR in both treatment groups using the multiple imputation procedures described in [Appendix A](#) (Steps 1-3). This process will be repeated 10 times.
2. To allow for MNAR in the reslizumab treatment group, a shift parameter will be used to adjust imputed values for OCS dose, by adding the shift parameter to the imputed values. The following pseudo-code is provided to demonstrate this concept, where OUTMI is the output dataset(s) from Step 1, COMPLETER identifies the patients who discontinued treatment early with incomplete follow-up, week24 is the OCS dose at week 24, and δ is the shift parameter.

```
data outmi;
  set outmi;
  if armcd='RESLIZUMAB' and COMPLETER='N' then week24=week24+ $\delta$ ;
run;
```

After this step, 10 datasets with complete data have been created.

3. The proportional odds model will be fitted to the complete set of data for each of the 10 datasets using the same covariates that were used for the primary analysis, following the outline described in [Appendix A](#) (Step 4).
4. Apply combining rules to the results from the 10 datasets using PROC MIANALYZE, as described in [Appendix A](#) (Step 5).
5. Repeat Steps 1-4 (above) using escalating values for the shift parameter resulting in estimates of the odds ratio and p-values for each shift parameter.

The odds ratio and associated p-value will be summarized corresponding to each selected shift value until the tipping point is achieved.

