9.6. Multiple Comparisons and Multiplicity

A fixed sequence multiple testing procedure will be implemented to test the primary and secondary variables while controlling the overall type I error rate at 0.05. If the resulting 2-sided p-value from the primary comparison is ≤ 0.05 , then the next comparison of interest (first secondary variable) will be interpreted inferentially at 0.05. This process continues through the secondary variables either until all comparisons of interest are interpreted inferentially or until

the point at which the resulting 2-sided p-value for a comparison of interest is >0.05 . At the point where $p>0.05$, no further comparisons will be interpreted inferentially. The hierarchy of endpoints is as defined in Section 9.5.2.

No multiplicity adjustments will be made for other efficacy and exploratory efficacy analyses.

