2.3. Sample Size and Power Considerations

The primary efficacy variable and endpoint for this study is the percent reduction in the daily OCS dose during weeks 20 to 24 as compared with the dose at the end of the optimization phase. The study will be considered positive if the measure meets statistical significance at the respective predefined significance level. A statistically significant effect of reslizumab over placebo, as measured by the primary efficacy variable, is required to establish the efficacy of reslizumab treatment.

The sample size was calculated based on the following assumptions:

- Categorical reduction in OCS dose after 24 weeks of treatment will have the following distribution for the placebo group (based on [Bel et al 2014](#)):
 - 10.9% percent of subjects will have 90% to 100% reduction
 - 7.9% percent of subjects will have 75% to <90% reduction
 - 14.8% percent of subjects will have 50% to <75% reduction
 - 10.8% percent of subjects will have 0% to <50% reduction
 - 55.6% percent of subjects will have no reduction, loss of asthma control, or discontinuation from study drug
- The overall odds ratio between reslizumab and placebo based on proportional odds model will be 2.63
- Alpha level of 0.05

Based on the above assumptions, a sample size of 76 subjects per group will provide 90% power to detect a significant effect of reslizumab over placebo on the probability for a higher categorical reduction of OCS dose.

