6.2.2. Primary Analysis

The primary endpoint is the 5-level categorical percent reduction in OCS dose during weeks 20 to 24, compared to the optimized dose at baseline. The primary analysis will incorporate data from all randomized patients. Patients who are unable to maintain asthma control or who

withdraw treatment prematurely will be analyzed as part of the lowest category of response. The primary endpoint will be analyzed using a proportional odds model including factors for treatment group and the randomization strata (age and OCS dose, as defined in Section 2.4); baseline OCS dose and duration of OCS use prior to study entry will also be included as covariates. Age and OCS dose will be based on data recorded in the clinical database.

The proportional odds ratio (reslizumab/placebo) will be estimated from this model, representing the ratio of the odds of a patient outcome being in a higher OCS dose reduction category for reslizumab compared to placebo. The estimated odds ratio, 95% CI, and p-value will be reported. A frequency distribution bar graph will be provided for the number of patients in each of the 5 categories by treatment group.

The following sample Statistical Analysis Software (SAS[®]) code pertains to the primary efficacy analysis of categorical dose reduction; ‘treatment’ is the randomized group (‘0’=placebo) and ‘out_cat5’ is the 5-level response category (1=worst category, ..., 5=best category):

```
proc genmod data=<<>> order=internal descending;
  class treatment (param=ref ref='0') strata1 strata2;
  model out_cat5 = treatment strata1 strata2 ocsbase ocsdur
    / dist=mult link=cumlogit aggregate=treatment type3;
  estimate "odds ratio" treatment 1 -1 / exp;
  ods output parameterestimates=<<>>;
run;
```

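### The Appendix B tipping-point search shifts only reslizumab doses, which saturate in the lowest category, so its stopping rule may be unreachable and placebo is never taken beyond MAR

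*SAP*

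**What the plan says.** **Primary analysis.** SAP 6.2.2 states that patients who lose asthma control or who "withdraw treatment prematurely will be analyzed as part of the lowest category of response". SAP 6.2.1 defines that category as no decrease, loss of control, or stopping study drug. The rule applies to both arms.

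**Tipping-point analysis.** SAP Appendix B runs only after a significant primary result. In it, "the OCS dose in the control group will be imputed assuming that missing data are MAR". Reslizumab doses are imputed in the same way and then raised by a constant, and "this shift will be progressively increased and the process repeated until the treatment effect is no longer significant at the 5% level". The code in step 2 applies the shift only to reslizumab patients who stopped treatment early and have incomplete follow-up. The shifted doses are converted to the five categories and the proportional odds model is refitted (Appendix A, step 4). Odds ratios and p-values are listed for each shift "until the tipping point is achieved".

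**Interpretation.** The one reading rule is that a tipping point at unreasonable values supports robustness. Appendix B gives no largest shift, no instruction for a result that never tips, and no placebo shift, although its opening describes a search over several combinations of imputed values.

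**Dropout.** Neither document gives an expected rate of discontinuation or of retrieval after discontinuation.

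**The concern.** A shift in mg can be raised without limit, but the outcome it feeds has a bottom category. Once every imputed reslizumab patient is there, a larger shift cannot alter the fit. That category is also where the primary analysis began. So on the reslizumab side the search runs from MAR back to the primary assumption and no further.

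The missing-data assumption that could most weaken a significant result is the placebo one. Placebo dropouts are scored worst in the primary analysis; if many of them had in fact reduced their dose, the treatment difference would shrink. Appendix B moves them to MAR and holds them there. At stake is the meaning of a report that no tipping point was found. It could reflect a robust result, or a search that ran out of room on one axis and never opened the other.

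**Working it through.** **1. The plan's own figure.** SAP 2.3 assumes a placebo distribution of 10.9/7.9/14.8/10.8/55.6%, best to worst (for the worst category, "55.6% percent of subjects will have no reduction, loss of asthma control, or discontinuation from study drug"). The same section sets the design effect at a proportional odds ratio of 2.63 and alpha at 0.05. Two-sided testing is from Protocol 9.6 ("If the resulting 2-sided p-value from the primary comparison").

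- Cumulative placebo proportions are 0.109, 0.188, 0.336, 0.444. Multiplying their odds by 2.63 gives 0.243, 0.378, 0.571, 0.677 for reslizumab, that is 24.3/13.5/19.3/10.6/32.3%.
- The arm averages are 17.6/10.7/17.0/10.7/43.9%; the sum of their cubes is 0.098.
- Whitehead: n per arm = 6(1.960 + 1.282)² / [(ln 2.63)² × (1 − 0.098)] = 6 × 10.51 / (0.935 × 0.902) = 74.7, so 75 against the stated 76.
- Power at 76: SE = √[6/(76 × 0.902)] = 0.296, and Φ(0.967/0.296 − 1.96) = 90.5%.

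The design figure reproduces.

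**2. Saturation.** The reduction after a shift δ is 100 × [baseline − (imputed + δ)] / baseline. The patient is at the floor once imputed + δ ≥ baseline. For a baseline of 20 mg and an imputed dose of 5 mg, the reduction is 75% at δ = 0, 50% at 5, 25% at 10, 0% at 15, and the same category at any larger δ. Baseline cannot exceed 40 mg (SAP Table 1, footnote b), so δ = 40 mg is enough for any non-negative imputed dose. The regression step states no lower limit, so a negative imputation may need slightly more, but still a finite amount.

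**3. Where the search starts and ends.**

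| Patients off drug | Primary | Appendix B, δ = 0 | Appendix B, end |
|---|---|---|---|
| Reslizumab, not followed | lowest | MAR | lowest |
| Placebo, not followed | lowest | MAR | MAR |
| Either arm, followed | lowest | observed dose | observed dose |

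The end scenario differs from the primary analysis only in rows two and three, and neither row is searched.

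**4. How often no shift tips a significant trial.** Assumed, since the documents are silent: dropout of 5–20%, equal in both arms, with all or half of it unretrieved; no covariates in the model. Category-level simulation: 2,000 trials per scenario, 76 per arm, 10 imputations, Rubin's rules, reslizumab at the infinite-shift limit. At odds ratio 2.63 with all dropout unretrieved:

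| Dropout | Placebo drawn from completers' full category mix | Placebo categorised on dose alone* |
|---|---|---|
| 5% | 93% | 90% |
| 10% | 84% | 74% |
| 15% | 72% | 58% |
| 20% | 55% | 37% |

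*Assumes half of the non-dropout lowest category is loss of control. This column is nearer to Appendix A, which categorises on the imputed dose.

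A dose-level simulation following Appendix A (250 trials per scenario, two modelling variants) gives 93–96%, 81–92% and 48–69% at 5%, 10% and 20% dropout, all unretrieved. One variant at 10% shows the plateau:

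| Shift (mg) | 0 | 5 | 10 | 20 | 40 | ∞ |
|---|---|---|---|---|---|---|
| Still significant (%) | 99.1 | 94.1 | 86.8 | 82.7 | 81.4 | 81.4 |
| Odds ratio (primary 2.72) | 2.89 | 2.51 | 2.31 | 2.18 | 2.17 | 2.17 |

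Other settings:
- Half of dropouts retrieved, odds ratio 2.63: about 74–98%.
- Odds ratio 2.0, 15–20% dropout, none retrieved: 16–45% at category level.

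**5. What a placebo axis would show** (odds ratio 2.63, category level). Taking placebo dropouts as far as the best category, a tipping boundary exists in these shares of significant trials (ranges are across repeat runs):
- None retrieved: 25–26%, 61–68% and 84–87% at 5%, 10% and 15% dropout.
- Half retrieved: 8–10%, 19–21% and 29%.
- Intermediate point, 10% dropout, none retrieved, placebo dropouts doing as well as reslizumab completers: 31% tip, against 19% one-way and 68% at the extreme corner in the same run.

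**The case against.** The end scenario is a demanding one. Reslizumab dropouts sit at the worst category while placebo dropouts move up from it, and the median odds ratio in significant trials falls from about 2.75 in the primary analysis to 1.7–2.6. A result that survives has passed a real test. Any bounded outcome has such an end, and because each shift is tabulated, a plateau would be visible. The extreme placebo corner is also implausible: it puts every placebo dropout at 90–100% reduction, where the design expects 10.9% of placebo patients. Protocol 4.5.1 asks for the week 24 OCS dose after stopping drug, which would leave few patients to impute. Appendix B is an outline, and it is one of several sensitivity analyses in SAP 6.2.3.

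All of this stands, and it limits three stronger readings that a reader might infer:

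- *That no shift can tip most significant trials.* This depends on dropout, retrieval and true effect. The documents give no dropout figure, and the statement fails at an odds ratio of 2.0 with 15–20% unretrieved dropout.
- *That the placebo assumption is untested.* Placebo dropouts are examined at two fixed points, the lowest category and MAR, and at observed doses where followed. They are not examined over a range or above MAR.
- *That a missing tipping point is only mechanical.* It also shows survival of the end scenario.

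The objection does not supply a stopping rule that always ends, or a placebo departure better than MAR.

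**Conclusion.** The point holds in a limited form. From the text alone, at any dropout rate: the shift is one-sided, it saturates in the category the primary analysis already uses, the stated stop can be unreachable, and no rule covers that outcome. Placebo is never explored beyond MAR.

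The frequency is conditional. At the design effect with up to about 15% unretrieved dropout, a majority of significant trials could not be tipped by any shift (58–93% at category level). At 20% unretrieved the figure is roughly 37–69% across both simulations. Retrieval of half the dropouts raises it. These figures rest on assumed dropout, equal rates in both arms, a model without covariates, and the narrower population in step 2; the prose before the steps refers more loosely to all who discontinued treatment, which would correspond to the all-unretrieved setting.

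The primary estimate, test and type I error are untouched. What needs repair is the robustness statement that would follow a significant result.

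**What to change.** Amend Appendix B, step 2, before database lock:

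- Use a two-way grid. On one axis add a shift to imputed reslizumab doses, as now; on the other subtract a shift from imputed placebo doses, with a floor of 0 mg.
- End each axis when all imputed patients in that arm are in the end category (lowest for reslizumab, best for placebo).
- Mark a reference point on the grid where placebo dropouts do as well as reslizumab completers, so that readers can judge plausibility.
- Report the odds ratios and p-values over the grid with the tipping boundary, or state that none exists.

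The cost is appendix wording and more runs of existing code; no data collection changes. The downside is small: the reported robustness may look weaker than under the one-way search.
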